4.6 Premature whole study termination

- Administrative problems e.g.: recurrent serious or severe ADR clinically evaluated by PI and/or sponsor as warranting whole study termination.
- A decision made by the sponsor and/or IRB/EC and/or local regulatory agency to terminate the study

4.7 Accountability procedures for the investigational products

Study drug will be dispensed by the pharmacy at the investigator's institution. The patient may be dispensed up to an 8 weeks supply of medication. The pharmacy must maintain an individual record of the patient. Drug dose, number of tablets received and returned must be recorded.

5 Selection and Withdrawal of Subjects

5.1 Inclusion Criteria

1. Heart failure patients with reduced ejection fraction ($EF \leq 40\%$) as assessed by echocardiography at least 6 months prior to recruitment and NYHA Class ≥ 2
2. Patients implanted with ICD, CRTD/S or CRTP devices that are capable of recording the PVC burden and implanted ≥ 2 months prior to recruitment.
3. High risk for arrhythmic events at baseline identified by either PVC burden $\geq 2\%$ **or** ≥ 2 events of non sustained VT **or** ≥ 1 event of sustained ventricular tachycardia **or** need for anti-tachycardia pacing **or** defibrillation therapy, during a period of 2 months prior to recruitment.
4. Diagnosis of type 2 diabetes mellitus prior to informed consent
5. $HbA_{1c} \geq 7\%$ and $\leq 12\%$.
6. Signed and dated written informed consent by date of Visit 1 in accordance with GCP legislation.

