
Primary endpoint:
	
The primary endpoint is the burden of premature ventricular complexes, defined as the PVCs percentage of all beats in a pre-specified period captured on ICD or CRTD/P device.

Secondary endpoints:
	
 1. The number of non-sustained ventricular tachycardia (NSVT) episodes. 2. A composite cumulative endpoint of ventricular arrhythmia load (number of: sustained ventricular tachycardia, ventricular fibrillation, antitachycardia pacing (ATP) or delivery of shock therapy episodes. 3. The change in blood level of NT-Pro Brain Natriuretic peptide (BNP) from baseline to the end of any of the treatment periods. 4. The change in Left ventricular end diastolic diameter on echocardiography from baseline to the end of any of the treatment periods. 5. The change in left ventricular ejection fraction (EF) on echocardiography from baseline to the end of any of the treatment periods. 6. Safety endpoints (as detailed bellow).

Study Design:
	
The present study is a randomized, prospective, controlled, double blind, cross-over, pairwise, add on standard therapy, event driven study, comparing empagliflozin versus placebo on the ventricular arrhythmia burden in a blocked randomization stratified by ischemic versus non-ischemic cardiomyopathy and PVC burden at screening of $<$ or \geq to 4%. Potential study subjects will sign an informed consent prior to undergoing any study related procedure. Number of patients to be enrolled is 128.
 
This study encompass 4 periods for each study subject: screening period of 8 weeks, first treatment period of 8 weeks, washout period of 4 weeks and a second treatment period of 8 weeks. Expected duration of subject participation is 6-7 months.
 
Study assessments will be performed according the table of study procedures below. (Table 2)
 
Screening period
 
Patients will undergo screening for protocol eligibility within 56 days (8 weeks) of recruitment.
 
Subjects meeting all the inclusion criteria and without any exclusion criteria will be enrolled after signing an informed consent.
 
Written informed consent must be obtained before any study specific medical procedures are performed. Evaluation consists of physical examination including vital signs, laboratory-

screening assessments including urine pregnancy test for FCBP, HbA_{1c}, device (ICD or CRTD/P) interrogation and echocardiography (if not done recently).

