4.2 Overall study design

The present study is a randomized, prospective, controlled, double blind, cross-over, pairwise, add on standard therapy, event driven study, comparing empagliflozin versus placebo on the ventricular arrhythmia burden in a blocked randomization stratified by ischemic versus non-ischemic cardiomyopathy and PVC burden at screening of $<$ or \geq to 4%.

Patients will be recruited from the congestive heart failure clinic of the study site and treated for up to 8 weeks with the study drug (or placebo) and then another 8 weeks with placebo (or study drug) with a washout period of 4 weeks between the two treatment periods. Potential study subjects will sign an informed consent prior to undergoing any study related procedure. Generally, study medications should be continued until intolerance. Treatment after completion of the study is at the discretion of the investigator.

Up to 128 patients are planned to be enrolled. Enrollment time of the study is one year.

This study encompass 4 periods for each study subject: screening period of 8 weeks, first treatment period of 8 weeks, washout period of 4 weeks and a second treatment period of 8 weeks. Expected duration of subject participation is 6-7 months.

Study assessments will be performed according the table of study procedures below. ([Table 2](#))

Screening / run in period

Patients will undergo screening for protocol eligibility within 56 days (8 weeks) of recruitment.

Subjects meeting all the inclusion criteria and do not meet any exclusion criteria will be enrolled after signing an informed consent.

Written informed consent must be obtained before any study specific medical procedures are performed. Evaluation consists of physical examination

including vital signs, laboratory-screening assessments including urine pregnancy test for FCBP, HbA_{1c}, device (ICD or CRTD/P) interrogation and echocardiography (if not done recently).

First treatment period

Randomization will take place after obtaining patient's informed consent and after fulfilling the inclusion and exclusion criteria. Patients will be assigned to empagliflozin or placebo treatment for a period of 8 weeks by a central randomization process.

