4.2.1 Visit schedule and assessments

Table 2 visit schedule and assessments

Trial Period	Screening	Treatment Period			
Visit	1	2	3	4	5
Study Week	0	8	16	20	28
Days from randomization	-56	0	56	84	140
Informed Consent	X				
Inclusion/Exclusion Criteria	X	X			
Medical History	X				
Concomitant therapy	X	X	X	X	X
Demographics	X				
Physical Exam	X	X			
Vital Signs	X	X	X	X	X
Height	X				
Weight	X	X	X	X	X
Randomization		X			
Pregnancy test ¹	X	X		X	X
Home Blood glucose monitoring ²		X	X	X	X
Safety blood samples ³	X	X	X		X
HbA _{1c}	X		X		X
Device Interrogation	X	X	X	X	X
Monitor Counter Reset	X	X	X	X	X
12 Lead Holter ECG for 24hrs		X	X		X
Echocardiography	X ⁴	X	X		X
NT-Pro-BNP		X	X	X	X
Medication Compliance check			X		X

¹ For female patients with childbearing potential (Urine pregnancy test).

[figure not shown]
² Patients without means for daily home blood glucose monitoring will be given a device on visit 2. Glucose level will be measured 3 times a day in the first week and thereafter once a week or as needed. Additional measurements are warranted in the case of hypo- or hyperglycemia signs or symptoms.

³ Safety blood samples include: Fasting blood samples (8hr fasting), Liver and kidney functions, urine dipstick for signs of infection and ketoacidosis (if positive leukocyte esterase (WBC) or nitrites a midstream urine sample for urine culture will be taken.

⁴ Echocardiography will be done if needed to verify patient suitability for inclusion criteria.

Trial Period	Screening	Treatment Period			
Visit	1	2	3	4	5
Study Week	0	8	16	20	28
Days from randomization	-56	0	56	84	140
Endocrinologist consult		X			
Biobank samples		X	X	X	X
Urine Analysis (Electrolytes)		X	X	X	X
24hr Urine Sample collection		X	X	X	X
CardioPulmonary Exercise Test & 6 minute walk distance ⁵		X	X		X
Adverse events		X	X	X	X

Study scheme

Visit 3
Analysis 1

Visit 5
Analysis 2

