7. Measure vital signs at screening in order to ensure compliance with study criteria. Vital signs measurements will include systolic and diastolic blood pressure, pulse rate, respiratory rate, and body temperature. Body weight and height will also be measured. Measurements that may potentially constitute future adverse events (e.g. hypoglycemia, hypotension etc.) should be graded in the medical history form at baseline according to CTC as described in [8.1.3 below](#).
8. Collect safety blood and urine samples. Including hematology and chemistry blood examinations and urine dipstick for signs of ketoacidosis or infection.
Hematology: Testing of Complete Blood Counts (CBC) including differential and platelet count will be performed at screening, in order to ensure compliance with study inclusion criteria (5 ml blood per sample). Every out-of-range value will be assessed by a physician and deemed as either clinically significant (S) or not significant (NS).
Chemistry: Serum chemistry panel will consist of sodium, potassium, calcium, protein, albumin, alanine aminotransferase (ALT), aspartate aminotransferase (AST), bilirubin, alkaline phosphatase, blood urea nitrogen (BUN), creatinine, and fasting glucose. Chemistry will be performed at screening, in order to ensure compliance with study inclusion criteria (5-10 ml blood per sample). Every out-of-range value will be assessed by a physician and deemed as either clinically significant (S) or not significant (NS).
11. Review menopausal status and in women of childbearing potential a urine pregnancy test (β -HCG) will be performed.
12. Collect venous blood will be drawn for HbA_{1c}.
13. Perform device interrogation by an electrophysiological technician for verification of arrhythmogenic risk according the eligibility criteria.
14. Perform monitor counter reset by an electrophysiological technician.
15. Perform echocardiography for verification of EF \leq 40% according to the eligibility criteria (if not done in the last 6 months).
16. Review concomitant medications. All prior treatments (medications) received by the subject within 30 days of the initial screening visit and during the study will be recorded on the subject's CRF including the name of the treatment, indication, total daily dose, frequency and the start and stop dates. Any medications (including prescription, over-the-counter, herbal supplements and health store products) to be taken during the study will be documented.

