Collection of information on standard of care treatment will be done as part of medications records during the study.

17. Invite study subject to study site for Holter ECG installation in one of the 7 days before the next visit.

Base line visit (2) (day 0 ±7 days)

1. Patient's enrollment. Eligibility for the study according to inclusion and exclusion criteria will be rechecked but lab tests not repeated) if all criteria are fulfilled and there is no significant change in the subject's health, he/she will be enrolled into the study to receive the first study drug.
2. Get patient randomization number.
3. Begin study drug treatment (active or placebo), provide patient 60 tablets and give treatment instructions for home use.
4. Perform a complete physical examination.
5. Measure vital signs in order to ensure compliance with study criteria. Vital signs measurements will include systolic and diastolic blood pressure, pulse rate, respiratory rate, and body temperature. Body weight will also be measured. Measurements that may potentially constitute future adverse events (e.g. hypertension, fever etc.) should be graded in the medical history form at baseline according to CTC as described in [8.1.3 below](#)
6. Collect safety blood and urine samples. Including hematology and chemistry blood examinations and urine dipstick for signs of ketoacidosis or infection.
7. Review menopausal status and in women of childbearing potential perform a urine pregnancy test (β -HCG).
8. Collect home diary glucose results and provide a new diary for the following period.
9. Provide home diary for daily blood glucose determination.
10. Perform device interrogation.
11. Perform Monitor counter reset.
12. Collect Holter ECG device results and invite study subject to study site for Holter ECG installation in one of the 7 days days before the next visit.
13. Perform echocardiography for determination of EF
14. Consult endocrinologist for glucose lowering medication titration
15. Collect blood examination for NT-Pro-BNP
16. Collect urine and blood examination for biobank sample
17. Collect urine for electrolyte concentration

18. Obtain 24 hours urine sample collection
19. Perform cardiopulmonary exercise test (In case of inability to perform cardiopulmonary exercise test according to clinical judgment, patient will have a 6 minute walk distance test)
20. Perform 6 minute walk distance
21. Review concomitant medications.
22. Document adverse events.

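### The 6-month limit on the qualifying echocardiogram runs in opposite directions in inclusion criterion 1 and in the screening procedure, and the protocol does not say which governs.

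*Combined protocol and SAP*

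**What the plan says.** Four places in the protocol bear on the age of the echo used for the EF criterion.

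- **Section 5.1, criterion 1.** EF must be 40% or below "as assessed by echocardiography at least 6 months prior to recruitment".
- **Section 4.2.2, screening visit, item 15.** An echo is performed at screening to check the 40% threshold "according to the eligibility criteria (if not done in the last 6 months"). A patient with an echo from the last 6 months need not be re-imaged; anyone else must be.
- **Synopsis and section 4.2.** Both list, among the screening evaluations, "echocardiography (if not done recently"). The term for recent is not defined.
- **Section 4.2.1, Table 2, footnote 4**, on the visit 1 echo: "Echocardiography will be done if needed to verify patient suitability for inclusion criteria".

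On timing, section 4.2 says: "Patients will undergo screening for protocol eligibility within 56 days (8 weeks) of recruitment". Table 2 puts visit 1 at day -56 and randomisation at day 0 (visit 2). An echo is also scheduled at visit 2, where the procedure list says "Perform echocardiography for determination of EF" and gives no threshold.

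**The concern.** Item 15 says it serves the eligibility criteria, so it and criterion 1 govern the same EF requirement. Yet one sets a minimum age for the echo and the other a maximum. A coordinator completing the eligibility form from 5.1 and one working from the visit procedures could reach different answers for the same patient.

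Reduced EF is part of the population named in the primary objective (section 3.1). The rule also decides who counts as an eligibility violation. Section 9.2 limits the per-protocol population to patients who completed in compliance with the protocol and had no major violations, and it does not say which eligibility failures are major. A literal audit against 5.1 could therefore flag patients who were screened exactly as item 15 directs.

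**Working it through.** The plan gives no figure on this point to reproduce. The check compares the texts and adds simple date arithmetic.

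**Is the literal reading of criterion 1 strained?** No. The same list in 5.1 expresses a minimum interval in criterion 2 (device implanted 2 months or more before recruitment) and a look-back window in criterion 3 (arrhythmic events over the 2 months before recruitment). The two ideas are worded differently, and criterion 1 takes the minimum-interval form.

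**Can one echo satisfy both rules?** Inputs: 6 months = 365.25 / 2 = 182.6, about 183 days; screening window = 56 days (section 4.2, Table 2). The protocol does not tie recruitment to a visit, so both possibilities are shown.

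- *Recruitment = visit 1.* Criterion 1 needs an echo age of about 183 days or more. Item 15 needs about 183 days or less. One echo meets both only at the boundary.
- *Recruitment = day 0, up to 56 days after visit 1.* Item 15 accepts an echo up to 183 days old at visit 1, which is up to 183 + 56 = 239 days old on day 0. Criterion 1 needs 183 days or more on day 0. One echo meets both only if it is about 183 to 239 days old on day 0.
- *A new echo done at screening under item 15* is 0 to 56 days old on day 0. It falls short of 183 days under either definition, so the protocol's own verification step cannot produce an echo that satisfies criterion 1 as written.

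**Which patients are classified differently?** Here, older means old enough for criterion 1, and recent means within the last 6 months or newly done at screening.

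| Echo record | 5.1 as written | Item 15 |
|---|---|---|
| EF 40% or below on both older and recent echo | met | verified |
| EF 40% or below on recent echo only | **not met** | **verified** |
| EF 40% or below on older echo, above 40% on recent | **met** | **not verified** |
| EF above 40% on both | not met | not verified |

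A patient with only an old qualifying echo is re-imaged under item 15 and then falls in row 1 or row 3. The rules disagree in rows 2 and 3. The documents give no distribution of EF or echo age, so the size of these groups cannot be calculated.

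**The case against.** The best counter-argument is that the passages are complementary. Section 5.1 would require reduced EF established some time ago, and item 15 would confirm that it persists. Meeting a historical criterion and then having a confirmatory echo is an ordinary sequence, and a patient in row 1 satisfies both. This reading is coherent, but no passage states it or asks for two qualifying echoes. Even if it is adopted, the row 2 patient passes item 15 and is still ineligible under 5.1. It is also possible that the wording of criterion 1 is a slip for a look-back window. The visible documents do not settle the intent. The synopsis list of inclusion criteria was not in the text available for this review, so it could not be checked for a clue.

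A reader might infer two stronger points, and the documents do not support either.

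- *That the protocol admits patients on an outdated EF.* This follows only if 5.1 is read alone. A site following the whole protocol re-images a patient whose only echo is old.
- *That the visit 2 echo plays no part in eligibility.* Table 2 schedules the eligibility check at visit 2 as well as visit 1. The visit 2 procedures recheck the criteria, exempt only laboratory tests from repetition, and measure EF at that visit. The echo is listed after enrolment and start of drug, but list order does not prove timing. The documents do not link the visit 2 EF to the threshold, and they do not exclude such a link.

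It is also fair to say that the consequences are limited. The crossover comparison of PVC burden is within patient, and EF is measured in everyone at visit 2, so the EF range actually enrolled will be documented.

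**Conclusion.** The point holds as an internal inconsistency in an operative eligibility rule. Criterion 1 and screening item 15 set the 6-month limit in opposite directions for the same threshold, no visible passage reconciles them, and the remaining screening text sides with item 15. Patients in rows 2 and 3 of the table are eligible under one passage and not under the other.

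The conclusion rests on the literal wording of both passages. It does not depend on whether recruitment means visit 1 or day 0: that choice only moves the overlap from a single boundary point to a window of about 56 days. The number of patients affected is unknown. Sample size, randomisation and the primary comparison are untouched. The effect is on the definition of the population, consistent screening, and the classification of deviations and of the per-protocol set. It is worth correcting, but it does not threaten the validity of the treatment comparison.

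**What to change.** Reconcile criterion 1 in section 5.1 with screening item 15 in section 4.2.2. Use one direction for the 6-month limit and one named reference date, either visit 1 or randomisation. Replace the undefined reference to a recent echo in the synopsis and section 4.2 with the same rule, and make Table 2 footnote 4 point to it. If long-standing reduced EF is also intended, state it as a separate criterion and say what happens when the older and the recent EF disagree. Which rule is right is for the investigators to decide.

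Carry the result into the eligibility form, with fields for the date and EF of the qualifying echo. If patients have already been enrolled, decide before unblinding how those in rows 2 and 3 will be classified for deviations and for the per-protocol set.

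The cost is small: one phrase in 5.1, matching wording in the other places, a change to the eligibility form, and the IRB approval that section 12.1 requires for a non-administrative amendment. No recalculation is needed.

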5.2 Exclusion Criteria

1. Evidence of ICD malfunction.
2. Antiarrhythmic treatment other than beta blockers.
3. Past exposure to SGLT2 inhibitors.
4. Uncontrolled diabetes with $HbA_{1c} > 12\%$ or glucose > 240 mg/dL after an overnight fast.
5. Liver abnormalities defined by serum levels of alanine aminotransferase, aspartate aminotransferase, or alkaline phosphatase above 3 x upper limit of normal.
6. Planned cardiac procedure within 3 months.
7. Prior MI in the last 40 days.

8. Calculated eGFR < 45ml/min/1.73m² as determined by the MDRD formula
$$\text{GFR (mL/min/1.73 m}^2\text{)} = 175 \times (\text{S}_{\text{cr}})^{-1.154} \times (\text{Age})^{-0.203} \times (0.742 \text{ if female}) \times (1.212 \text{ if African American})$$
9. BMI > 50
10. Medical History of active cancer in the last 2 years. Exceptions include the following: Basal cell carcinoma of the skin, Squamous cell carcinoma of the skin, Carcinoma *in situ* of the cervix, Carcinoma *in situ* of the breast, Incidental histologic finding of prostate cancer (TNM stage of T1a or T1b).
11. History of recurrent UTIs or genital infections
12. Systolic blood pressure < 90mmHg.
13. Alcohol or drug abuse within 3 months of informed consent.
14. Pre-menopausal women (last menstruation <+ 1 year prior to informed consent) who:
 - are nursing or pregnant or
 - are of child-bearing potential and are not practicing an acceptable method of birth control, or do not plan to continue using this method throughout the study and do not agree to submit to periodic pregnancy testing during participation in the trial. Acceptable methods of birth control include tubal ligation, transdermal patch, intra uterine devices/systems, oral, implantable or injectable contraceptives, sexual abstinence, double barrier method and vasectomised partner.
15. Intake of an investigational drug in another trial within 30 days prior to intake of study medication in this trial or participating in another trial involving an investigational drug and/or follow-up

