(ischemic versus non-ischemic) and the left ventricular EF⁷. The introduction of defibrillation therapy for primary prevention of SCD in HF patients has revolutionized the field during the last 2 decades. Nevertheless, ventricular arrhythmias still remain a major cause of mortality for HF patients given the limited ability for risk stratification, and the dreadful prognosis associated with ventricular arrhythmias treated by defibrillation therapy^{8,9}. The burden of premature ventricular Complexes (PVCs) has been shown as an independent risk factor for ventricular tachyarrhythmia and SCD for healthy, ischemic and heart failure patients (with and without resynchronization and/or defibrillator therapy).¹⁰⁻¹⁹ Anti-arrhythmic drugs (AAD) are efficient in suppressing the occurrence of PVCs but for certain drugs, the associated with profile of adverse events and cardiotoxicity may paradoxically increase the rate of sudden cardiac death as learned by the remarkable CAST study.²⁰ Be that as it may, easily suppressed PVC burden (without the associated adverse profile of AADs) has been suggested to correlate with reduction of the likelihood for SCD²¹. Furthermore, the growing field of PVC ablation has been shown to have beneficial effect on cardiac function and the risk for ventricular arrhythmia²². In summary, PVC suppression, a once neglected strategy, is now considered a promising strategy for evaluating the effect of therapeutic strategies on the risk for SCD²³.

Empagliflozin treatment in high cardiovascular risk patients with diabetes has been shown to have a relatively rapid powerful capability in reducing cardiovascular mortality. Among the suggested mechanisms mediating this effect of empagliflozin, anti-arrhythmic effect (AAE) has the highest potential to translate into a rapid clinical beneficial effect on cardiovascular mortality, while other mechanisms are known to have a lag in their clinical effect based on data from previous studies. Based on this assumption, we hypothesize that the effect of empagliflozin on the rate of cardiovascular death may be mediated by a direct effect on the risk for arrhythmic events (via a direct or an indirect effect on the myocardium). The current study aims at assessing the effect of empagliflozin on arrhythmias in diabetes patients with HF with reduced EF and relatively high arrhythmic burden.

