Treatment washout visit (3) (day 56 ±7 days)

1. Provide patient with 30 tablets of study drug for home use
2. Collect study drug blisters returned by patient.
3. Measure vital signs in order to ensure compliance with study criteria. Vital signs measurements will include systolic and diastolic blood pressure, pulse rate, respiratory rate, and body temperature. Body weight will also be measured.
4. Collect safety blood and urine samples. Including hematology and chemistry blood examinations and urine dipstick for signs of ketoacidosis or infection.
5. Remind patient to follow the endocrinologist instructions given on visit 2.
6. Collect venous blood that will be drawn for HbA1c.
7. Collect home diary glucose results and provide a new diary for the following period.
8. Perform device interrogation.
9. Perform Monitor counter reset.
10. Collect Holter ECG device results and invite study subject to study site for Holter ECG installation in one of the 7 days days before the next visit.
11. Perform echocardiography for determination of EF
12. Collect blood examination for NT-Pro-BNP
13. Collect urine and blood examination for biobank sample
14. Collect urine for electrolyte concentration
15. Obtain 24 hours urine sample collection
16. Perform cardiopulmonary exercise test (In case of inability to perform cardiopulmonary exercise test according to clinical judgment , patient will have a 6 minute walk distance test)

17. Perform 6 minute walk distance
18. Review concomitant medications.
19. Document adverse events.

Treatment visit (4) (day 84 ±7 days)

1. Provide patient with 60 tablets of study drug for home use
2. Collect study drug blisters returned by patient.
3. Measure vital signs in order to ensure compliance with study criteria. Vital signs measurements will include systolic and diastolic blood pressure, pulse rate, respiratory rate, and body temperature. Body weight will also be measured.
4. Review menopausal status and in women of childbearing potential perform a urine pregnancy test (β -HCG).
5. Remind patient to follow the endocrinologist instructions given on visit 2.
6. Collect home diary glucose results and provide a new diary for the following period.
7. Perform device interrogation.
8. Perform Monitor counter reset.
9. Collect blood examination for NT-Pro-BNP
10. Collect urine and blood examination for biobank sample
11. Collect urine for electrolyte concentration
12. Obtain 24 hours urine sample collection
13. Review concomitant medications

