14. Document adverse events.

End of Study visit (5) (day 140 ±7 days)

- 1.
2. Collect study drug blisters returned by patient.
3. Measure vital signs in order to ensure compliance with study criteria. Vital signs measurements will include systolic and diastolic blood pressure, pulse rate, respiratory rate, and body temperature. Body weight will also be measured.
4. Collect safety blood and urine samples. Including hematology and chemistry blood examinations and urine dipstick for signs of ketoacidosis or infection.
5. Review menopausal status and in women of childbearing potential perform a urine pregnancy test (β -HCG).
6. Collect venous blood that will be drawn for HbA1c.

7. Collect home diary glucose results.
8. Perform device interrogation.
9. Perform Monitor counter reset.
10. Collect Holter ECG device results.
11. Perform echocardiography for determination of EF
12. Collect blood examination for NT-Pro-BNP
13. Collect urine and blood examination for biobank sample
14. Collect urine for electrolyte concentration
15. Obtain 24 hours urine sample collection
16. Perform cardiopulmonary exercise test (In case of inability to perform cardiopulmonary exercise test according to clinical judgment , patient will have a 6 minute walk distance test)
17. Perform 6 minute walk distance.
18. Review concomitant medications.
19. Document adverse events.

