7.1 PVCs Burden

The primary efficacy parameter to be assessed will be PVCs burden.

PVCs burden is defined as the PVCs percentage of all beats in a pre-specified period captured on ICD or CRTD/P device.

PVCs burden will be evaluated as a part of the device interrogation on visit 1 to assess device integrity and proper function, in visit 2 to assess patient's eligibility for the study according to in- and exclusion criteria. In visits 3 and 5 to assess for treatment efficacy.

Assessment of the PVCs will be based on PVC counters for the various ICD/CRTD/P interrogated (from Medtronic, St. Jude, Guidant – Boston Scientific, Biotronik). Monitor counter reset will be conducted on visit 1,2,3,4 and 5. The equation for calculating the PVC burden for monitoring providing the PVC number per period will be:

$$PVC\ Burden(\%) = \frac{Number\ of\ PVCs}{Average\ HR\ \left(\frac{beats}{minute}\right) * 60 * 24 * (\#days\ in\ the\ period\ assessed)}$$

For monitors providing the PVC burden per hour the calculation will be:

$$PVC\ Burden(\%) = \frac{Average\ \frac{PVC}{hour}}{Average\ Heart\ Rate\left(\frac{Beats}{Minute}\right) * 60}$$

In case of device malfunction, counter malfunction or any other cause of inability to readout the device PVC counter measurement, PVC burden will be

calculated from a 12 Lead ECG Holter for 24 hours conducted at one of the last 7 days of the period assessed and will be calculated as:

$$PVC\ Burden(\%) = \frac{Number\ of\ PVCs}{Average\ Heart\ Rate\ \left(\frac{beats}{minute}\right) * 60 * 24}$$

Monitor counter readout and resetting will be performed by an electrophysiologist technician; data will be entered into the CRF by the study coordinator after approval of the principal investigator.

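### Exclusion 6 bars cardiac procedures planned within 3 months, but the second measured period runs to day 140, so a procedure already booked for most of period 2 is not excluded

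*Combined protocol and SAP*

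**What the plan says.** Exclusion 6 in section 5.2 is a single line: "Planned cardiac procedure within 3 months". It does not say whether the 3 months run from consent, visit 1 or randomisation.

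Section 4.2 sets out a "screening period of 8 weeks, first treatment period of 8 weeks, washout period of 4 weeks and a second treatment period of 8 weeks" and adds: "Expected duration of subject participation is 6-7 months". Table 2 places visit 1 at day -56, visit 2 at day 0, visit 3 at day 56, visit 4 at day 84 and visit 5 at day 140. Section 4.2.2 gives visits 2 to 5 a window of 7 days either way.

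Eligibility is checked twice. At visit 2, "Eligibility for the study according to inclusion and exclusion criteria will be rechecked", and Table 2 marks the criteria at both visits 1 and 2.

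PVC burden, the primary endpoint, comes from device counters reset at every visit (section 7.1): "In visits 3 and 5 to assess for treatment efficacy". Each reading therefore summarises a whole treatment period.

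On procedures during the study:

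- Section 4.5 lists reasons for ending participation, including device malfunction, myocardial infarction and need for an antiarrhythmic drug. It does not list a cardiac procedure.
- Section 6.2 allows therapies needed for supportive care and safety.
- Section 9.2 has no rule for PVC data recorded after a procedure.
- Section 4.4.1 lets the investigator stop treatment for other reasons.
- The synopsis lists concomitant procedures among the safety assessments.

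The background (section 2.2) says that "the growing field of PVC ablation has been shown to have beneficial effect on cardiac function and the risk for ventricular arrhythmia".

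**The concern.** A two-period crossover relies on each patient being in a comparable state in both periods. Exclusion 6 is evidently meant to protect that, but its horizon is shorter than the schedule it has to protect. A patient booked for an ablation in, say, month 4 after randomisation meets the criteria as written. The period 2 counter would then mix beats from before and after the procedure, and the change would enter that patient's empagliflozin-placebo difference under whichever treatment was given in period 2. The visit 5 echocardiography and NT-proBNP values would be exposed in the same way.

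The protocol takes care elsewhere to keep antiarrhythmic influences out: antiarrhythmic drugs other than beta blockers are an exclusion, are not permitted during the study, and the need for one is an exit reason. A planned ablation late in the study gets no matching treatment. Section 9.1 states no dropout allowance and section 4.4.1 says withdrawn subjects are not replaced, so the 80% power has no reserve.

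**Working it through.** **Inputs.** Window: 3 months, taken as 91 days (section 5.2). Treatment days: 0-56 and 84-140 from randomisation (Table 2). Planning values: difference 10, SD of differences 40, N = 128, two-sided alpha 0.05 (section 9.1).

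**1. The plan's own figure.** Noncentrality = 10 / (40/√128) = 2.828. The noncentral t gives power 80.1% with 126 df and 80.2% with 127 df, so the stated 80% at N = 128 is reproduced.

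**2. Where the window ends.**

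- From the visit 2 recheck: 0 + 91 = day 91. Period 1 and the washout are covered. Uncovered in period 2: 140 − 91 = 49 of 56 days. Taking 90 or 92 days gives 50 or 48.
- From visit 1 only: −56 + 91 = day 35, which would leave the last 21 days of period 1 and all 56 days of period 2 uncovered.

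**3. What would cover the schedule.** From visit 1 to visit 5 is 56 + 140 = 196 days (28 weeks, about 6.4 months), or 203 days with the 7-day allowance at visit 5. From visit 2 it is 140 days (about 4.6 months), or 147 with the allowance. The stated window is about 91.

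**4. How much of a procedure's effect reaches the endpoint.** The counter averages over the period, so a procedure on day d with full effect D shifts the period 2 reading by D × (140 − d)/56. With d uniform over days 91-140, the fraction (140 − d)/56 is uniform from 0 to 49/56 = 0.875. Its mean is 0.4375 and its mean square is 0.875²/3 = 0.2552.

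**5. Effect on power.** Sequence is randomised 1:1, so the shift enters the empagliflozin-placebo difference with either sign equally often. With a fraction f of patients affected, SD = √(1600 + f × 0.2552 × D²). For D = 80 units, 0.2552 × 6400 ≈ 1633. Power is from the noncentral t with 127 df.

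| f (assumed) | SD of differences | Power |
|---|---|---|
| 0 | 40.0 | 80% |
| 2% | √(1600 + 32.7) = 40.4 | 79% |
| 5% | √(1600 + 81.7) = 41.0 | 78% |
| 10% | √(1600 + 163.3) = 42.0 | 76% |

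With D = 100 units (complete abolition, if the planning scale is percent reduction), 0.2552 × 10,000 ≈ 2552 and power is 79%, 77% and 74%. With D = 40 units it is 80%, 80% and 79%. The documents give neither f nor D, and the uniform dates are also an assumption.

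**6. If affected patients are left out instead.** N falls to 125, 122 or 115 at 2%, 5% or 10%, and power (N − 2 df) to 79%, 78% or 76%.

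**The case against.** The strongest reply is that the gap is narrow and its effect slight. Much of that stands.

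- A reader might infer that 77 of the 112 treatment days (69%) are open, by counting 3 months from visit 1. The documents do not support that as the working figure. Criteria are rechecked at visit 2, so a procedure booked within 3 months of day 0 fails there. The gap is days 91-140.
- A reader might infer a large loss of power. If every affected patient's difference moved by a full 80 units, power would be 77%, 73% or 66% at rates of 2%, 5% or 10%. But the counter averages over the period, and no procedure in the open window can affect more than 87.5% of it. On an absolute percentage-point scale, an 80-unit shift would also be hard to square with the 2% entry and 4% stratification thresholds.
- A reader might infer bias for or against empagliflozin. The booking exists before randomisation to sequence, so the direction is balanced in expectation. The signed-rank test named in section 9.1 also limits how far a few extreme patients can drive the result.
- A reader might infer that the patient must stay in the trial. Section 4.4.1 permits discontinuation at the investigator's discretion. That is a possible route out, not a rule, and may be applied unevenly.
- A reader might extend the point to revascularisation, device upgrade or generator change. An effect of these on PVC burden is plausible, but the documents state an arrhythmia effect only for ablation. Section 7.1 provides a Holter backup where a counter cannot be read.

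None of this closes the gap: no section excludes, or says how to handle, a procedure planned for days 91-140.

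**Conclusion.** The point holds as a minor one. The exclusion window and the visit schedule do not match: on the reading most favourable to the plan, 49 of the 56 days of period 2 are uncovered, and sections 4.5, 6.2 and 9.2 are silent on a planned procedure in that time. The mismatch follows from the documents alone, apart from taking 3 months as 91 days.

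The consequence is added variance and some patients whose two periods are not comparable. Its size rests on assumptions: at 2-10% of patients, a full effect of 80 units and uniform dates, the cost is roughly 1 to 4 points of power. With no procedure rate in the documents, nothing larger can be claimed.

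**What to change.** Reconcile the exclusion window with the visit schedule. Reword exclusion 6 in section 5.2, and the matching synopsis item if it reads the same, to: *Cardiac procedure planned at any time before Visit 5*, checked at visits 1 and 2. Tying the limit to visit 5 removes the undefined start point and absorbs the 7-day visit allowance.

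This is a cheap improvement: one line of eligibility text and no change to the design, visits or sample size. The cost is that a few patients with a procedure booked later in the study are deferred until after it or not enrolled. It does not deal with unplanned procedures, for which section 9.2 would still have no data-handling rule.
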